9.3 POPULATIONS FOR ANALYSES

Every effort will be made to ensure all enrolled and randomized participants complete all study sessions as described in this protocol. However, a priori, we determined that our population for analysis will be a modified intention-to-treat (ITT) analysis dataset. For this study, enrolled eligible participants will be randomized to receive 40 minutes of stimulation. If a participant completes the intervention (i.e., completes the first session), they will be included in all analyses moving forward.

As previously stated in **Section 7 Study Intervention Discontinuation and Participant Discontinuation/Withdrawal**, enrolled participants who do not complete session 1 will be replaced. Therefore, with this population for analysis plan, we anticipate having data from 48 participants that are eligible for analysis.

9.4 STATISTICAL ANALYSES

9.4.1 GENERAL APPROACH

All testing described below assumes a significance threshold of $p = 0.05$. Analyses will be deemed to be statistically significant if the p -value is less than this threshold. An analysis that does not exceed this threshold will be considered inconclusive. Continuous data will be described using means, standard deviations, and confidence intervals, while categorical data will be described using counts/percentages.

There may be additional covariates included in the analysis. Data will be assessed for normality and, if deemed necessary, corrective procedures will be applied (e.g., log normalization). Based on our previous dataset, we expect that the variables used here will be approximately Gaussian. However, if the distribution of a variable displays a skewed tail and a test for normality fails, then it is justified to use a corrective procedure. This correction will be applied upon consideration of the variables themselves, and not based on the result of the intended analysis.

Data will be collected until 48 participants complete the first session and all data is usable. Given that there is only a single session, we expect to have complete data and all analyses will include the full participant pool. However, if there are technical errors that are not caught in time, then the affected analyses may have less participants. In this scenario, the data for a participant is then completely removed from the analysis. We emphasize that lost data is typically of greater concern for longitudinal and multi-session studies. If a subset of participants does not complete the second session in this experiment, then only the analysis of exploratory outcome 2 will be affected.

9.4.2 ANALYSIS OF THE PRIMARY OUTCOME (BEHAVIOR)

Goal-directed behavior will be calculated as the average decision to perform the HARD task. The average for the four blocks prior to stimulation and the four blocks during stimulation will be calculated. A two-way analysis of covariance (ANCOVA) will be performed using within-participant factor of time (before or during stimulation), between-participant factor stimulation type (delta-beta tACS, theta-gamma tACS, or active-sham), and anhedonia symptom severity as a linear covariate (SHAPS at session 1 as a continuous variable). We hypothesize to find an interaction between time and stimulation type in the ANCOVA. Post-hoc differences will be investigated using Tukey's test. We hypothesize that the predicted interaction will be driven by an increase in goal-directed behavior for delta-

beta tACS. Sensitivity analyses will be conducted to evaluate the specificity of these effects: a similar analysis with reward-evaluation as the dependent variable and we do not expect that delta-beta tACS will have any effect on reward-evaluation.

Furthermore, we hypothesize that the inclusion of the SHAPS covariate is critical to our findings in that participants with the greatest symptoms of anhedonia will demonstrate the greatest increase to goal-directed behavior. This effect will be investigated by a correlation between the baseline symptoms of anhedonia (SHAPS) and the change in goal-directed behavior for participants that received delta-beta tACS. The specificity of this effect will be investigated as a difference in correlation between the relationship of anhedonia symptoms and goal-directed behavior for the group that received sham tACS.

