In the second session, participants provide written consent to participate in the study. Then, participants are randomized into one of three arms of the study: delta-beta tACS, control tACS in theta-gamma, or active sham. Randomization is stratified by SHAPS level such that there are an equal number of participants that are high anhedonia (SHAPS > 33) and low anhedonia (SHAPS ≤ 33). We expect that of the 48 participants in the final dataset, there will be 8 from each of the 6 groups (3 stimulation conditions by 2 anhedonia levels). Two 4.5 by 4.5 centimeters stimulation pads are applied to the scalp over the left hemisphere anterior and ventral to F3 and posterior and ventral to C3, and a 5 by 7 centimeters stimulation pad is applied centered over FCz in an anterior to posterior direction. Prior to any task performance, participants under eyes-closed and eyes-open resting-state while fixating on a central point on the monitor. Participants complete titration of the difficult of the EEfRT. Then, participants perform 4 blocks of the EEfRT during the collection of EEG. After each block of the EEfRT, there is a 2 minute eyes-open resting-state scan. Next, participants receive tACS during performance of the EEfRT. Delta-beta tACS, theta-gamma tACS, or sham-tACS is received during task performance. Stimulation is turned off between blocks, and eyes-open resting-state EEG is acquired. The total amount of stimulation is approximately 40 minutes for 8 blocks that

each last approximately 5 minutes. After tACS, participants complete a stimulation side effects questionnaire and a blinding questionnaire. A blinding questionnaire is completed by the experimenter. The blinding questionnaire is a single question that asks whether the participant receive stimulation or placebo, and then asks the participant to provide an explanation for their response. Based on the results of the stimulation side effects questionnaire, a structured adverse events interview is conducted to acquire more information regarding any side effects that were selected to be "very high" by the participant.

[figure not shown]

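### The SHAPS term in 9.4.2 and 9.4.3 is not fully specified: read literally it drops out of the time-by-stimulation test, and software that adds SHAPS-by-time gives a different result

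*Combined protocol and SAP*

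**What the plan says.** Section 9.4.2 reduces the primary outcome to one mean before and one mean during stimulation. The model is then set out: "A two-way analysis of covariance (ANCOVA) will be performed using within-participant factor of time (before or during stimulation"), a between-participant factor for the three stimulation types, and "anhedonia symptom severity as a linear covariate (SHAPS at session 1 as a continuous variable"). The effect of interest is stated plainly: "We hypothesize to find an interaction between time and stimulation type in the ANCOVA". Section 9.4.3 repeats the same model and hypothesis for delta-beta coupling. Neither section names a SHAPS-by-time term, a SHAPS-by-stimulation term or a three-way term, and neither gives the software or how the covariate is to be handled.

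For the primary outcome only, 9.4.2 adds that "the inclusion of the SHAPS covariate is critical to our findings", because the most anhedonic participants are expected to gain most. That expectation has its own analysis: "This effect will be investigated by a correlation between the baseline symptoms of anhedonia (SHAPS) and the change in goal-directed behavior" in the delta-beta arm, followed by a comparison with sham ("The specificity of this effect will be investigated as a difference in correlation"). Section 4.1 says "Randomization is stratified by SHAPS level", split at 33, with 8 participants expected in each of six cells. Section 9.4.1 removes a participant with lost data completely from the affected analysis, so before/during pairs are complete.

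**The concern.** With two time levels, the time-by-stimulation interaction is a comparison between arms of each person's change. A covariate that takes one value per person and enters as a main effect shifts both time points equally and subtracts out of that change. The model then lists SHAPS while the hypothesised test makes no use of it.

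The wording also fits a second model. A repeated-measures ANCOVA fitted as a multivariate general linear model carries covariate-by-time as well, and there SHAPS does alter the interaction F, its estimates and its degrees of freedom. Two analysts who follow the text faithfully could therefore report different p-values for the primary test, and likewise for the secondary one. At stake are a pre-specified primary test that is not uniquely defined and some precision from a baseline score that is already collected.

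**Working it through.** **1. Algebra.** Write participant i's value at time t as Y_it = (arm, time and arm-by-time effects) + β·SHAPS_i + u_i + e_it. The change is D_i = Y_i,during − Y_i,before. Both β·SHAPS_i and u_i cancel, so D_i depends only on arm and residual error. The interaction F is the one-way F on D_i with 2 and 48 − 3 = 45 degrees of freedom, with or without the SHAPS main effect. If SHAPS-by-time is added, D_i gains a term γ·SHAPS_i and the test has 2 and 44 degrees of freedom.

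**2. Numerical check** on one simulated 48-person data set, 16 per arm, used only to confirm the cancellation and not as a measure of size:

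| Model | Interaction estimates | F |
|---|---|---|
| time × arm | −2.76546, −1.87607 | 0.40149 |
| time × arm + SHAPS | −2.76546, −1.87607 | 0.40149 |
| time × arm + SHAPS × time | −2.23695, −1.42144 | 0.25372 |

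The first two rows agree exactly and the third differs. In a single data set F may move either way.

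**3. The plan's own power figure.** Inputs from section 9.2: N = 48, 3 groups, 2 measurements, effect 0.288, correlation 0.5; the 0.05 significance threshold is from 9.4.1. No covariate enters the calculation. For a within-between interaction, λ = f²·N·m/(1 − ρ) = 0.288² × 48 × 2 / 0.5 = 15.93. With df 2, 45 the power is 94.2%, against a stated 93%. At ρ = 0.7 the smallest N for 80% power is 21, as stated. Both figures come out only if 0.288 is used as Cohen's f, although section 9.2 labels it partial eta-squared. That is a separate matter; λ = 15.93 is used here only as the protocol's working value.

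**4. Power with SHAPS-by-time, slope common to all arms.** If SHAPS correlates r with change, the residual variance of change falls by r² and λ becomes λ/(1 − r²), with df 2, 44. The documents give no r, so a range of 0 to 0.5 is assumed. The 70% starting point (λ = 8.24) is also an assumption, to show a less well powered case.

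| r | λ from 15.93 | Power, from 94.2% | λ from 8.24 | Power, from 70% |
|---|---|---|---|---|
| 0 | 15.93 | 94.2% | 8.24 | 69.9% |
| 0.3 | 17.50 | 96.0% | 9.05 | 74.3% |
| 0.5 | 21.23 | 98.4% | 10.98 | 82.5% |

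**5. Slope in the delta-beta arm only.** Section 9.4.2 predicts the SHAPS relation for delta-beta and a difference from sham. Take a slope of b SD of change per SD of SHAPS in that arm and zero in the other two (assumed). The pooled variance of change is 1 + b²/3, the fitted common slope is b/3, and the share of variance removed is (b/3)²/(1 + b²/3).

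- b = 0.5: 0.0278/1.0833 = 2.6%, so power goes from 70% to 71%.
- b = 0.8: 0.0711/1.2133 = 5.9%, so power goes from 70% to 73%.

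**6. How often the two readings disagree.** In 4,000 simulated trials per scenario, 16 per arm, with an effect giving 70% power, the two models fell on opposite sides of p = 0.05 in 4%, 10% and 17% of trials at r = 0, 0.3 and 0.5. Type I error was about 5% under both.

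**The case against.** The strongest reply is that little harm follows. Randomisation is stratified on SHAPS at 33, so arms are balanced on that split by design and the unadjusted comparison of change is unbiased. The sample size assumes no gain from SHAPS. The relation that the protocol predicts is specific to delta-beta, and a common slope captures little of it (step 5). All of this stands, and it limits the size of the point.

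Three stronger readings are tempting, and the documents do not support them.

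- A reader might infer that SHAPS has no effect anywhere in the analysis. Even as a main effect it can alter the stimulation main effect and between-arm comparisons at a single time point, and under routines that add covariate-by-time it alters the interaction as well.
- A reader might take "we hypothesize that the inclusion of the SHAPS covariate is critical to our findings" as a claim that the ANCOVA covariate drives the result. In context it is a statement about moderation, with its own correlation and comparison with sham. It is made for the primary outcome only; 9.4.3 contains nothing like it.
- A reader might infer bias or an inflated false-positive rate. Neither follows.

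What the reply does not answer is that the text permits two models with different F statistics and does not choose between them.

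**Conclusion.** The point holds in a limited form. On the literal main-effect reading, with complete pairs, SHAPS cannot influence the hypothesised interaction test in either section, so that test is unadjusted for the stratification variable. On the other permissible reading it is adjusted. The primary and secondary tests are therefore not uniquely determined by the plan.

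The precision at stake is 0 to about 4 percentage points of power at the protocol's own noncentrality, and 0 to about 13 points from an assumed 70% if the slope is common to all arms. It is only 1 to 3 points from 70% if the slope is confined to delta-beta. These figures rest on assumed SHAPS-change associations, 16 participants per arm and complete data. The firmer ground for changing the text is the undetermined test; the gain in precision is secondary.

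**What to change.** In 9.4.2 and 9.4.3, name centred session-1 SHAPS-by-time as a model term, or equivalently regress the change score on arm and SHAPS. State that the time-by-stimulation test is read from that model whatever software is used. The planned SHAPS correlation and its comparison with sham can stay as the separate moderation analysis.

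The cost is about one sentence in each section and one residual degree of freedom (45 to 44). If SHAPS is unrelated to change, power moves from 70% to 69.9%, which is negligible. No new data are needed.

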9.4.4 ANALYSIS OF THE EXPLORATORY OUTCOMES

First exploratory outcome: symptom dimensions

A two-dimension factor analysis will be run on all sub-scores from clinical assessments to derive a mood and motivation composite symptom score. This analysis was used in our previous study and found that goal-directed behavior negatively correlated with motivation symptoms. Thus, we hypothesize that the severity of motivation symptoms will correlate with the degree to which delta-beta tACS will increase goal-directed behavior. The analysis will be run as a Pearson correlation within the group that received delta-beta tACS. To control for the specificity of this effect, this correlation will be compared to sham tACS, mood symptoms, and reward-evaluation.

Second exploratory outcome: functional connectivity in frontal-striatal circuitry

Using the resting-state functional magnetic resonance imaging data, we will calculate the strength of functional connectivity between the dorsal striatum and the lateral prefrontal cortex. We hypothesize that participants with major depressive disorder and anhedonia will show decreased strength in connectivity, and that individual differences in this functional connectivity strength will be predictive of the change in goal-directed behavior with delta-beta tACS. The analysis will be run as a Pearson correlation within the group that received delta-beta tACS. To control for the specificity of this effect, this correlation will be compared to sham tACS and reward-evaluation.

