4.3 JUSTIFICATION FOR DOSE

Transcranial alternating current stimulation (tACS) is an extremely safe non-invasive stimulation paradigm without a single serious adverse event directly related to stimulation. The same tACS method has been used during performance of a task with intermittent resting-state EEG in our previous approved UNC IRB protocol 18-0003 (NCT03800030) that was overseen by [name]. A similar experimental design using a single session with reward-based

decision-making tasks and tACS in participants with major depressive disorder (MDD) was approved in our previous UNC IRB protocol 16-1911 (NCT03449979) that was overseen by [name]. Transcranial Alternating Current Stimulation (tACS) applies a weak electric current to the scalp and all previous studies (approximately 15 to date) performed in the Carolina Centers for Neuroimaging and Neuroinformatics at UNC IRB. Thus, no direct FDA oversight is required and no investigational device application filing is required. Further conversations with the regulatory core of the UNC CTSA and the director of the Office of Human Research Ethics that administers the UNC IRB over the years have consistently confirmed this classification.

tACS will be delivered using a cross-frequency stimulation waveform delta-beta (3-20Hz), a control frequency of theta-gamma (5-50Hz), or sham in which stimulation is delivered in either delta-beta or theta-gamma for 10 seconds and then returns to baseline (Figure 1). These waveforms were designed based on our previous experiment that observed these brain activity patterns in a reward-based decision-making task in participants with MDD. The stimulation amplitude delivered is standard for tACS studies (Ahn, Mellin et al. 2018, Alexander, Alagapan et al. 2019) – stimulation peaks at 1 mA during the peak of the high-frequency component for target electrodes (see Y-axis of Figure 2). The high frequency component consists of 3.5 cycles of a sine-wave of the high frequency that is centered at 90 degrees of each cycle of the low-frequency component. Stimulation peaks at 2 mA zero-to-peak for the return electrode, but the electrode size is 35 cm² for the return electrode and 20.25 cm² for each of the target electrodes. Thus, the current density is comparable between the two: 0.057 mA/cm² for the return electrode and 0.049 mA/cm² for the target electrodes.

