9.1 STATISTICAL HYPOTHESES

- Primary Outcome hypothesis:
 - Null: There is no difference in goal-directed behavior between baseline EEFRT and EEFRT during stimulation as a function of stimulation type (delta-beta tACS, theta-gamma tACS, or active-sham).
 - Alternate: There is a difference in goal-directed behavior between baseline EEFRT and EEFRT during stimulation as a function of stimulation type (delta-beta tACS, theta-gamma tACS, or active-sham).
- Secondary Outcome hypothesis:
 - Null: There is no difference in delta-beta phase-amplitude coupling strength between prefrontal electrodes and left motor electrodes for post-stimulation resting-state periods as a function of stimulation type (delta-beta tACS, theta-gamma tACS, or active-sham).

- Alternate: There is a difference in delta-beta phase-amplitude coupling strength between prefrontal electrodes and left motor electrodes for post-stimulation resting-state periods as a function of stimulation type (delta-beta tACS, theta-gamma tACS, or active-sham).
- Exploratory Outcome hypothesis 1:
 - Null: The impact of delta-beta tACS on goal-directed behavior is not correlated with motivation symptom severity.
 - Alternative: The impact of delta-beta tACS on goal-directed behavior is correlated with motivation symptom severity.
- Exploratory Outcome hypothesis 2:
 - Null: Functional connectivity during the resting-state between dorsal striatum and lateral prefrontal cortex is not predictive of the impact of delta-beta tACS on goal-directed behavior.
 - Alternative: Functional connectivity during the resting-state between dorsal striatum and lateral prefrontal cortex is predictive of the impact of delta-beta tACS on goal-directed behavior.

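### The specificity checks on the symptom and connectivity correlations use sham as the only comparator arm, so a link common to active tACS could be read as specific to delta-beta

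*Combined protocol and SAP*

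**What the plan says.** Section 4.1 randomises participants to "delta-beta tACS, control tACS in theta-gamma, or active sham", and 4.3 describes theta-gamma as the control frequency.

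For both exploratory outcomes, 9.4.4 states: "The analysis will be run as a Pearson correlation within the group that received delta-beta tACS". The predictor is the motivation symptom score in outcome 1 and frontal-striatal connectivity in outcome 2. The check on outcome 1 reads: "To control for the specificity of this effect, this correlation will be compared to sham tACS, mood symptoms, and reward-evaluation". For outcome 2, "this correlation will be compared to sham tACS and reward-evaluation".

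Section 9.4.2 follows the primary analysis with a correlation between baseline SHAPS and change in goal-directed behavior in the delta-beta arm. Its specificity is examined as a difference from the relationship between "anhedonia symptoms and goal-directed behavior for the group that received sham tACS".

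The theta-gamma arm appears in none of these three comparisons. It is one of the three levels of stimulation type in the ANCOVAs of 9.4.2 and 9.4.3.

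**The concern.** A contrast with sham asks whether a link appears under active stimulation. It does not ask whether the link belongs to the delta-beta frequency. Under 6.1.2 the two active arms have the same amplitude, the same ramps and the same 40 minutes of stimulation, whereas sham current is left on only briefly. Delta-beta against sham therefore mixes frequency with amount of current, and only delta-beta against theta-gamma separates them.

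The rival explanation is not far-fetched. Section 4.2 reports that in the earlier study both waveforms engaged their targets and modulated behavior, so the control arm cannot be assumed inert. If motivation symptoms, connectivity or SHAPS predicted response to either waveform, the listed checks would not reveal it.

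What is at stake is interpretation. Section 4.1 says the exploratory analyses enabled by the MRI session will inform the design of future studies, and 4.2 says the results may feed into interventions for anhedonia. A mistaken attribution to frequency could carry forward into both.

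**Working it through.** The documents give no sample size, power or effect size for these correlations, so there is no stated figure to reproduce. The check is a reading of the text followed by an illustration of size.

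**Which comparisons are planned**

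| Correlation with change in goal-directed behavior | Section | Comparator arm | Other comparators |
|---|---|---|---|
| Motivation symptoms | 9.4.4, outcome 1 | sham | mood symptoms, reward-evaluation |
| Frontal-striatal connectivity | 9.4.4, outcome 2 | sham | reward-evaluation |
| SHAPS | 9.4.2 | sham | none named |

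Mood symptoms replace the predictor and reward-evaluation replaces the outcome. Neither changes the stimulation frequency. The ANCOVAs include theta-gamma but compare mean change between arms. SHAPS enters them as a linear covariate, and no term is stated that lets its slope differ by arm. No section compares any of the three correlations with theta-gamma.

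**Inputs for the illustration**
- Participants per arm: 48 / 3 = 16, or two strata of 8 (4.1).
- Alpha: 0.05 (9.4.1). Sidedness is not stated, so two-sided is assumed.
- True correlation: not in the documents, so varied from 0.3 to 0.8.
- Decision rule: not in the documents. Assumed here: the delta-beta r is significant and exceeds the sham r by a Fisher z test.
- Mood and reward-evaluation checks: not modelled.

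**Formulas**
- Single-arm threshold: r = t / sqrt(t² + n − 2). With n = 16 (14 df), |r| must reach 0.497.
- Difference between two arms: SE of the Fisher z difference = sqrt(1/13 + 1/13) = 0.392.
- Observed r needed to differ from an observed 0: tanh(1.96 × 0.392) = 0.646.
- True r against 0 detectable with 80% power: tanh((1.96 + 0.842) × 0.392), about 0.80.

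**Simulation** (200,000 runs, bivariate normal data, three arms of 16)

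| Assumed r | Shared link passes sham check | Shared link also exceeds theta-gamma | Truly delta-beta-only link passes both |
|---|---|---|---|
| 0.3 | 8.3% | 1.3% | 4.0% |
| 0.5 | 26.3% | 1.9% | 15.4% |
| 0.6 | 41.8% | 2.1% | 27.7% |
| 0.7 | 61.4% | 2.3% | 46.7% |
| 0.8 | 82.1% | 2.4% | 71.9% |

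In the middle columns the link is equal in both active arms and zero in sham. In the last column it is zero in theta-gamma as well. The sham-only check never looks at theta-gamma, so its pass rate is the same whether the link is shared or confined to delta-beta. It cannot tell the two apart at any r.

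**What a failed theta-gamma contrast means**

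Suppose the link truly is delta-beta-only. Among trials that pass the sham check, the share that then fails the theta-gamma contrast is:
- r = 0.5: (26.3 − 15.4) / 26.3 = 41%
- r = 0.6: (41.8 − 27.7) / 41.8 = 34%
- r = 0.7: (61.4 − 46.7) / 61.4 = 24%

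A non-significant contrast at this sample size is therefore weak evidence that an effect is shared.

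**The case against.** Section 9.4.4 speaks of specificity without saying that it means frequency, and two of its three checks for outcome 1 concern symptom or behavior. The alternative hypothesis in 9.1, "The impact of delta-beta tACS on goal-directed behavior is correlated with motivation symptom severity", stays true even if theta-gamma shows the same link. The sample-size section frames both main outcomes relative to placebo, so sham is a consistent reference. Active sham is designed to mimic skin sensation, which weakens sensation as the shared mechanism. Because theta-gamma may modulate behavior itself, a correlation in that arm could have its own cause. The illustration uses a decision rule that the plan does not state and omits two listed checks. If those checks were required, they could only lower the pass rates.

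Most of this stands, and it limits the claim. A reader might infer that the plan will declare delta-beta specificity whenever the correlation exceeds sham. The documents set no such rule, so the supportable statement is that a shared link could be read that way. A reader might also infer that the trial neglects its control arm. It does not, because both ANCOVAs include theta-gamma, with Tukey comparisons, and so address frequency for the mean effect.

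What the objection does not remove is that the only arm differing from delta-beta in frequency alone is missing from the checks on these correlations.

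**Conclusion.** The point holds in limited form. In all three places sham is the sole comparator arm, and the remaining checks do not address frequency.

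The 8% to 82% range depends on the assumed true correlation, on exact equality between the active arms, on a zero correlation in sham, on the assumed decision rule and on 16 per arm. It illustrates the exposure and does not predict an error rate for this trial. For outcome 2 the number per arm may be below 16, because 4.1 does not require the MRI session for a complete dataset.

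One further inference should be resisted: that a link exceeding sham but not significantly exceeding theta-gamma is a general effect of active tACS. Section 9.4.1 treats a non-significant analysis as inconclusive, and the power available here gives no reason to depart from that.

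The consequence is confined to exploratory analyses and one follow-up correlation in a pilot study. This is a cheap improvement, not a threat to the main conclusions.

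**What to change.** For both exploratory outcomes in 9.4.4, and for the SHAPS correlation in 9.4.2:
- Compare the delta-beta correlation with theta-gamma tACS as well as with sham.
- Report each arm's correlation, and the delta-beta minus theta-gamma difference with a confidence interval. One model of change with an arm-by-predictor interaction would serve equally well.
- Call a link specific to delta-beta only if the theta-gamma contrast supports it. If the link exceeds sham but that contrast is not significant, report frequency-specificity as inconclusive.

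Changing 9.4.4 alone would leave the SHAPS check in 9.4.2 with the same gap.

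The cost is one extra low-power contrast per analysis. The theta-gamma symptom scores and behavior are collected in any case, as are scans where the MRI session is completed. Fewer specificity claims will follow. When the link truly is delta-beta-only, about 15%, 28% and 47% of trials would support the claim at r = 0.5, 0.6 and 0.7, instead of 26%, 42% and 61%. That is a reason to present the contrast as estimation, not to leave it out.
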